8.1.2 Serious Adverse Advents

Investigators should report AEs that meet the definition of an SAE (see Appendix 6 for definition) and are not excluded from the reporting process as described below.

8.1.2.1 Events that do not require reporting on a Serious Adverse Event Form

The following events should not be reported on an SAE Form:

- Disease progression
- Hospitalisations for:

- o Protocol defined treatment
- o Pre-planned elective procedures unless the condition worsens
- o Treatment for progression of the patient's cancer

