Clinical evidence that the mTOR pathway is important in DLBCL pathogenesis includes two recent phase II trials. 77 'aggressive' NHLs received everolimus in the relapsed, refractory setting (11). ORR was similar in mantle cell lymphoma (MCL), follicular lymphoma (FL) and DLBCL patients (32%, 38% and 30% respectively), demonstrating significant activity albeit in a minority of patients. The University of Chicago group (12), reported an ORR 28.1% (CR 12.5%) in a relapsed, refractory DLBCL subpopulation, with a median PFS of 2.6 months and OS of 7.2 months. Everolimus attenuated S6RP phosphorylation in a dose-dependent manner in DLBCL cell lines. Cell proliferation was inhibited, but minimal apoptosis was observed. This data provides a proof of principle, although responses were modest and resistant was frequent. The same group investigated mTOR inhibitor resistance pathways in DLBCL, and demonstrated that when DLBCL cells are treated with rapamycin, cells activate AKT through mTORC2 signalling; providing an escape mechanism (13). A variety of methods to attempt to overcome rapamycin resistance have been investigated, with some promising results. Wanner et al (10) demonstrated that everolimus induced G1-phase arrest in DLBCL cell lines and augmented cytotoxicity induced by rituximab. Moreover, a recent study showed that in DLBCL patients with PI3K/AKT/mTOR activation, outcomes were considerably inferior if rituximab was not added to CHOP (14). The group found that when rituximab was combined with rapamycin in DLBCL cell lines from these patients, that there was synergistic in vitro down-regulation of PI3K/AKT/mTOR signalling by Western blotting. Rituximab down-regulated PI3K/AKT/mTOR activation that had otherwise correlated with a more aggressive clinical course with poor treatment response.

A recent phase II study of everolimus combined with rituximab examined the efficacy and tolerability in relapsed/refractory DLBCL ineligible for, or relapsing after, autologous stem cell transplant (ASCT). 75% were considered rituximab-refractory at enrolment. Everolimus 10mg/d was given with rituximab 375mg/m² weekly for four weeks and then every four weeks. 26 patients displayed an ORR of 38% [90% CI (21-56%) with 3 CRs and 6 PRs]. OS was 37% at 12 months and the regimen was well tolerated.

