8. ADVERSE EVENT REPORTING

The collection and reporting of Adverse Events (AEs) will be in accordance with the Medicines for Human Use Clinical Trials Regulations 2004 and its subsequent amendments. Definitions of different types of AE are listed in Appendix 5. The Investigator should assess the seriousness and causality (relatedness) of all AEs experienced by the patient (this should be documented in the source data) with reference to the Investigator Brochure.

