8.2.2 Trials Office

On receipt of an SAE Form seriousness and causality will be determined independently by a Clinical Coordinator. An SAE judged by the Investigator or Clinical Coordinator to have a reasonable causal relationship with the trial medication will be regarded as a Serious Adverse Reaction (SAR). The Clinical Coordinator will also assess all SARs for expectedness. If the event meets the definition of a SAR that is unexpected (i.e. is not defined in the RSI/ Investigator Brochure) it will be classified as a Suspected Unexpected Serious Adverse Reaction (SUSAR).

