8.2.5 Safety Monitoring Committee

The Trial Safety Committee (TSC) will review all SAEs.

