APPENDIX 5- DEFINITION OF ADVERSE EVENTS

Adverse Event

Any untoward medical occurrence in a patient or clinical trial subject administered a medicinal product and which does not necessarily have a causal relationship with this treatment. Comment:

An AE can therefore be any unfavourable and unintended sign (including abnormal laboratory findings), symptom or disease temporally associated with the use of an investigational medicinal product, whether or not related to the investigational medicinal product.

Please note this does not include abnormal laboratory findings. An abnormal laboratory value is only considered to be an AE if the abnormality:

- Results in early discontinuation from the study treatment and/or
- Requires study drug dose modification or interruption, any other therapeutic intervention, or is judged to be of significant clinical importance
- Is Hyperglycaemia of > 1 week or if the investigator considers the rise in glucose to be medically significant

If a laboratory abnormality is one component of a diagnosis or syndrome, then only the diagnosis or syndrome should be recorded.

Pre-existing events should only be classified as AEs if they worsen by at least one grade from screening.

Adverse Reaction

All untoward and unintended responses to an IMP related to any dose administered.

Comment:

An AE judged by either the reporting Investigator or Sponsor as having causal relationship to the IMP qualifies as an AR. The expression reasonable causal relationship means to convey in general that there is evidence or argument to suggest a causal relationship.

Serious Adverse Event

Any untoward medical occurrence or effect that at any dose:

- Results in death
- Is life-threatening*
- Requires hospitalisation** or prolongation of existing inpatients' hospitalisation
- Results in persistent or significant disability or incapacity
- Is a congenital anomaly/birth defect
- Or is otherwise considered medically significant by the Investigator***

Comments:

The term severe is often used to describe the intensity (severity) of a specific event. This is not the same as serious, which is based on patients/event outcome or action criteria.

* Life threatening in the definition of an SAE refers to an event in which the patient was at risk of death at the time of the event; it does not refer to an event that hypothetically might have caused death if it were more severe.

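### The SAE exemption for disease progression is silent on fatal cases, so a death on treatment or within 30 days that the site attributes to lymphoma gets no independent causality check

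*Protocol*

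**What the plan says.** Section 8.1.2 asks investigators to report AEs that meet the SAE definition and "are not excluded from the reporting process as described below". Section 8.1.2.1 then introduces its list with "The following events should not be reported on an SAE Form". The first entry is disease progression. The list also covers admissions for "Treatment for progression of the patient's cancer". Its only qualifier concerns elective procedures where the condition worsens; no entry mentions death.

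The SAE definition in Appendix 5 has as its first criterion "Results in death".

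On who judges cause, section 8 states: "The Investigator should assess the seriousness and causality (relatedness) of all AEs experienced by the patient". Section 8.2.2 adds a second opinion: "On receipt of an SAE Form seriousness and causality will be determined independently by a Clinical Coordinator". Section 8.2.5 reads: "The Trial Safety Committee (TSC) will review all SAEs". Section 8.1.3 sets the AE reporting period from the start of protocol treatment to 30 days after the last dose, and again excepts the events listed earlier.

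**The concern.** The second opinion in 8.2.2 exists so that the site's view of causality does not stand alone. For a death the site calls progression, it does stand alone, because no form is sent and nothing else starts the review.

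Misattribution is foreseeable here. Section 1.2.3.2 lists pneumonitis and infections among the AZD2014 risks, and section 7.7 names tumour lysis syndrome for patients with high tumour burden. Section 7.5.2.5 itself treats disease progression as a competing explanation for new respiratory symptoms. With a single arm there is no control death rate against which an excess would show.

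At stake is whether a drug contribution to an early death is recognised. SAR and SUSAR classification follows from the same assessment in 8.2.2, so the reports in 8.2.3 depend on it too. The matter weighs most in the six-patient combination stage, where a judgement on tolerability is made after three patients.

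**Working it through.** The point concerns a reporting rule, and the plan states no figure for it. The check is mainly a reading of the sections together.

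**The chain for a death within the 30-day window that the site attributes to lymphoma**

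1. Appendix 5: the event is serious, because it is fatal.
2. 8.1.2: a serious event is reported unless excluded, so an exclusion overrides step 1.
3. 8.1.2.1: disease progression is excluded without qualification, so on a plain reading no SAE form is sent.
4. 8.2.2: independent causality starts when a form arrives. No other trigger is stated.
5. 8.2.5: the committee's review of individual events is defined on SAEs.
6. 8.1.3: the listed events are excepted from AE reporting as well, so the AE form is not a clear fallback.

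**What still captures the death**

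- 12.1.2: death from any cause is an event for OS and PFS. Cause is not adjudicated. After progression, survival status is collected 6-monthly (7.10) or annually (section 3), against 24 hours for an SAE (8.2.1.2).
- 13.4: the committee monitors all safety and primary activity data at its scheduled meetings. The protocol does not say that it receives a listing of deaths with attributed cause.
- 12.2: scans are reviewed centrally. That checks the imaging, not the cause of death.

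None of these routes assigns causality independently.

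**Illustration of how many early deaths there might be**

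The input is a phase II study cited in section 1.1 for relapsed DLBCL, "with a median PFS of 2.6 months and OS of 7.2 months". Assumptions that are not in the protocol: exponential times, every patient progresses before death, and treatment stops at progression.

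- Mean post-progression survival = (7.2 − 2.6) / ln 2 = 4.6 / 0.693 = 6.64 months.
- 30 days = 0.986 months. P(death within 30 days) = 1 − exp(−0.986 / 6.64) = 13.8%, that is 0.138 × 30 = 4.1 or 0.138 × 36 = 5.0 patients.
- If the mean is 4 months: 1 − exp(−0.986 / 4) = 21.8%, or 7.9 of 36.
- If the mean is 10 months: 1 − exp(−0.986 / 10) = 9.4%, or 3.4 of 36.

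The range is about 3 to 8 of 36. This counts all early deaths, whatever their cause.

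**What one reclassified death does to a reported toxicity rate**

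Section 12.2 reports toxicity proportions with 95% confidence intervals. The exact (Clopper-Pearson) upper limit for 0 of 30 is 1 − 0.025^(1/30) = 11.6%. For 1 of 30 it is the p at which P(X ≤ 1) = 0.025, which is 17.2%. No decision rule in the protocol uses this limit; it shows only how sensitive a rare-event rate is in a sample of 30.

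**The case against.** Progression is an efficacy endpoint here, and keeping it off SAE forms is coherent. That stands, and the exemption for non-fatal progression should remain.

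A reader might infer that these deaths bypass the Trial Safety Committee, or that it decides on SAE data alone. The text does not support this. Section 13.4 gives it all safety data, section 12.4 bases interim stopping on a pragmatic assessment of all outcomes, and the tolerability rule in 12.6 counts toxicities causing delays or dose modifications in the first two cycles, not SAEs. What is lost is review of the death as an individual event.

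A reader might also infer that toxic deaths go unseen. Every death is an OS and PFS event, and AE forms are completed at each visit with the highest grade since the last (8.2.1.1), so an infection or respiratory event before the death should be on record. A fatal infection, pneumonitis or tumour lysis also stays reportable as an SAE; it escapes only if the site labels it progression.

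That the exemption reaches fatal cases is inferred from the absence of an exception, not stated. The SAE Form Completion Guidelines in the Investigator Site File, to which 8.2.1.2 refers, may deal with it; they are not at hand.

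The illustrative count is also open to criticism: an exponential PFS followed by an exponential post-progression time does not give an exponential OS, so the model is approximate at best. It says nothing about how many deaths are toxic or misattributed.

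What remains after all this is that no described route gives such a death a causality opinion from outside the site.

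**Conclusion.** The gap is real and narrow. As written, a death on treatment or within 30 days of the last dose that the site attributes to lymphoma receives no independent causality assessment and no event-level committee review. What can be missed is a drug contribution to the death, not the death itself.

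The number of misattributed deaths cannot be estimated from the documents. The 3 to 8 of 36 describes only how many early deaths might occur under the assumed exponential times, and should not be read as a count of missed toxic deaths. No design figure for activity or tolerability changes.

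The conclusion rests on reading the unqualified exemption as covering fatal cases, and on no other document available to sites overriding it. This is a cheap safety improvement to a stated rule, not an error in the design. It belongs in the protocol, because an analysis plan cannot recover causality assessments that were never made.

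**What to change.** In 8.1.2.1, limit the exemption to non-fatal progression, keep the exemption for hospital stays to treat it, and add a sentence such as: any death from the first dose until 30 days after the last dose is reported on an SAE form, whatever cause the site gives. The exception in 8.1.3 should be worded to match. The Clinical Coordinator then assigns causality under 8.2.2 and the committee reviews each such death under 8.2.5.

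The window is the one already set in 8.1.3, and both reviews already exist, so no new procedure or staff is needed. The cost is a handful of extra SAE forms (3 to 8 under the illustration above, fewer if some of those deaths are already reported under another cause), most of which can be expected to confirm progression.

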8.1.2.2 Monitoring pregnancies for potential Serious Adverse Events

It is important to monitor the outcome of pregnancies of patients in order to provide SAE data on congenital anomalies or birth defects.

In the event that a patient or their partner becomes pregnant during the SAE reporting period please complete a Pregnancy Notification Form (providing the patient's details) and return to the Trials Office as soon as possible. The patient should be given a release of medical information form or the patient should be asked to give this to their partner. If the patient/partner is happy to provide information on the outcome of their pregnancy they should sign the release of medical information form. Once consent has been obtained provide details of the outcome of the pregnancy on a follow-up Pregnancy Notification Form and if necessary also complete an SAE Form.

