5.3 Contraception

For patients receiving AZD2014 only

Females of and males with partners of childbearing potential must use adequate methods of contraception.

- *Females* of child-bearing potential to use 2 forms of contraception (1 highly effective method and 1 barrier method), from registration to 4 weeks after trial treatment discontinuation. Please note that use of oral, injected or implanted hormonal methods may not be highly effective as it is unknown if AZD2014 will reduce their effectiveness.
- *Males* should be surgically sterile or willing to use an effective method of barrier contraception and refrain from sperm donation from first treatment until 16 weeks after trial treatment discontinuation

For patients receiving rituximab

Contraception should be used from registration until at least 12 months following treatment discontinuation.

For patients to be classed as having evidence of non-child-bearing potential they must fulfill one of the following criteria at screening:

- Post-menopausal defined as amenorrhoeic for at least 12 consecutive months following cessation of all exogenous hormonal treatments. If under 50 Serum follicle-stimulating hormone (FSH) and luteinizing hormone (LH) levels must be in the postmenopausal range
- Documentation of irreversible surgical sterilisation by hysterectomy, bilateral oophorectomy or bilateral salpingectomy, but not tubal ligation

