8.1.3 Reporting period

Details of all AEs (except those listed above) will be documented and reported from the date of commencement of protocol defined treatment until 30 days after the administration of the last treatment.

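### Pregnancy notification stops 30 days after last treatment, short of the protocol's own contraception period for men on AZD2014 alone and for rituximab patients

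*Protocol*

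**What the plan says.** Section 8.1.2.2 explains that pregnancy outcomes are monitored to supply SAE data on congenital anomalies and birth defects. It then gives the trigger: "In the event that a patient or their partner becomes pregnant during the SAE reporting period please complete a Pregnancy Notification Form". The same section provides for a release form and a follow-up form for the outcome.

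The term SAE reporting period is not defined separately. Section 8.1.3, headed Reporting period and worded for AEs in general, is the only definition available: "from the date of commencement of protocol defined treatment until 30 days after the administration of the last treatment".

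Section 5.3 sets three contraception periods:

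- Women on AZD2014 alone: "from registration to 4 weeks after trial treatment discontinuation".
- Men on AZD2014 alone: "from first treatment until 16 weeks after trial treatment discontinuation".
- Patients receiving rituximab: "Contraception should be used from registration until at least 12 months following treatment discontinuation".

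Section 8.1.4 keeps SAEs reportable without a time limit if they are both at least possibly related and unexpected. Appendix 5 lists a congenital anomaly or birth defect among the SAE criteria.

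**The concern.** The contraception periods in section 5.3 are the protocol's own statement of how long conception should be avoided after treatment. For two of the three groups they run well past the point at which the duty to notify a pregnancy ends. A partner pregnancy beginning 10 weeks after a man's last AZD2014 dose, or a pregnancy 6 months after the end of combination treatment, would fall inside the period in which the protocol asks for contraception. Yet it would start neither the notification form nor the outcome follow-up.

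At stake is the purpose that section 8.1.2.2 gives for itself. A birth defect usually becomes apparent months after conception, so the notification form is the step that would lead the site to the outcome. No efficacy endpoint, decision rule or sample-size figure is affected.

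**Working it through.** The plan gives no figure of its own here, so the check is a comparison of windows in days.

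**Inputs**

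- Notification ends 30 days after last treatment (8.1.2.2 with 8.1.3).
- Contraception after discontinuation (5.3): 4 weeks = 28 days for women on AZD2014 alone; 16 weeks = 112 days for men on AZD2014 alone; at least 12 months, taken as 365 days, for rituximab patients.
- Group sizes (section 3): 30 on AZD2014 alone, 6 on AZD2014 plus rituximab.
- Discontinuation is taken as the date of the last dose.

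**Post-treatment gap**

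Uncovered days = max(0, contraception window − 30).

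| Group | Window (days) | Uncovered (days) | Share |
|---|---|---|---|
| Women, AZD2014 alone | 28 | 0 | 0% |
| Men, AZD2014 alone | 112 | 112 − 30 = 82 | 82/112 = 73% |
| Rituximab patients | 365 | 365 − 30 = 335 | 335/365 = 92% |

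**How far the rituximab figure depends on the clock**

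Section 7.2 gives rituximab for 6 cycles, while AZD2014 continues until progression, toxicity or patient choice. Section 5.3 does not say which drug's discontinuation starts the 12 months. If the last rituximab dose starts them and AZD2014 continues for A further days, the reporting period also runs on, and the gap is max(0, 365 − (A + 30)) = max(0, 335 − A). For A = 56 that is 279 days, for A = 168 it is 167 days, and at A = 335 or more it is zero. So 335 days applies when both drugs stop together or when the clock starts at the last dose of trial treatment. With 12 months taken as exactly 365 days, it is the upper end.

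**Including time on treatment**

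Days on treatment (T) are inside the reporting period. Over treatment plus the post-treatment window, the uncovered share is uncovered days / (T + window). The documents give no expected T, so the values below are assumptions, and the rituximab row uses the 335-day case.

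| Group | T = 28 | T = 56 | T = 168 | T = 365 |
|---|---|---|---|---|
| Men, AZD2014 alone: 82/(T + 112) | 59% | 49% | 29% | 17% |
| Rituximab patients: 335/(T + 365) | 85% | 80% | 63% | 46% |

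More than half is uncovered only if T is below 2 × 82 − 112 = 52 days (men, AZD2014 alone) or 2 × 335 − 365 = 305 days (rituximab).

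**Start of the window**

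For women and for rituximab patients contraception starts at registration, but reporting starts at first treatment. Section 6 allows up to 7 days between the two. No trial drug has been given in that interval, and the schedule in 7.3 has a pregnancy test within 7 days before cycle 1 day 1, so this gap is minor.

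**Does another clause close the gap?**

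Section 8.1.4 would still take in a related and unexpected anomaly that came to light later. It creates no duty to record a pregnancy, obtain the release form or follow the outcome.

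**The case against.** Several objections carry weight.

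- A reader might infer that most at-risk pregnancies would go uncollected. The documents do not support that. The shares are days of a window. No pregnancy rate, sex split or treatment duration is given, and contraception is required throughout. Once treatment time is counted, the uncovered part for men on AZD2014 alone falls to half or less from 52 days of treatment.
- A reader might also infer that a report of no pregnancies would describe only 30 days. It would describe the whole treatment period plus 30 days.
- Section 5.3 sets precautions. It does not call them a risk window or a surveillance period, so aligning the two is a reasonable inference, not the protocol's wording. Reading the SAE reporting period as the one in 8.1.3 is also an inference, though no alternative is offered and SAEs are AEs.
- The 12-month period concerns 6 of 36 patients, and pregnancy data are not an outcome measure.
- Section 8.1.4 gives partial cover. The SAE Form Completion Guidelines and the Drug Supply Agreement, to which the protocol refers, are not at hand and might add duties.

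These points limit the size of the problem. They do not remove the mismatch: within the protocol text, nothing requires a form for a pregnancy that begins after day 30 but inside the contraception period.

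**Conclusion.** The point holds as a reconciliation of sections 5.3, 8.1.2.2 and 8.1.3. As written, the notification rule undercuts its stated aim for men on AZD2014 alone, where 82 of 112 post-treatment days (73%) are uncovered, and for the 6 rituximab patients, where up to 335 of 365 days (92%) are. Women on AZD2014 alone have no post-treatment gap. The figures rest on reading 8.1.3 as the SAE reporting period, on equating discontinuation with last dose, on counting 12 months as 365 days and, for rituximab, on starting the 12 months at the last dose of trial treatment. If the last rituximab dose starts them while AZD2014 continues, the gap is smaller and can vanish. Few events are expected. This is a safety-reporting gap that is worth correcting because each exposed pregnancy is informative and the correction is cheap. It says nothing about how many pregnancies would be missed.

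**What to change.** In section 8.1.2.2, replace the reference to the SAE reporting period with a window that runs from registration to the end of the contraception period that applies to the patient under section 5.3. Keep the existing outcome follow-up form. State in section 5.3 which drug's discontinuation starts the rituximab period, so that the end of the window can be determined. Leave the AE reporting period in 8.1.3 unchanged, with a cross-reference to the separate pregnancy window.

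The cost is a few sentences of protocol text, an instruction to patients and possibly a few extra forms. The instruction is needed because section 7.10 does not guarantee contact with the patient throughout the longer window. Its one-year minimum runs from the start of treatment, follow-up after progression is for survival data, and after a progression-free year it is the registering physician who is contacted every 6 months. Patients should therefore be told to inform the site of any pregnancy, their own or a partner's, that begins within the applicable period. No dose, contraception rule or analysis changes.
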